#### 9.4.2 ANALYSIS OF THE PRIMARY EFFICACY ENDPOINT(S)

See above

---

#### 9.4.3 ANALYSIS OF THE SECONDARY ENDPOINT(S)

No analysis needed- endpoint is simple measurement.

---

#### 9.4.4 SAFETY ANALYSES

First, we will rigorously analyze the kava product prior to use to ensure its consistent quality with no flavokavains A and B. Second, we have implemented stringent exclusion criteria and will provide education to the enrolled subjects to minimize potential drug-herb interactions. Third, we will monitor participants throughout the study and for 12 weeks following the end of treatment to ensure that any potential acute or delayed adverse effects are identified and addressed. Serum liver chemistries (AST, ALT, ALP, bilirubin (total, direct, and indirect) and albumin, Prothrombin Time and International Normalized Ratio) will be drawn at baseline, post treatment, and every 4 weeks following treatment up to 12 weeks. The adverse events checklist will be completed at each of these visits as well.

---

#### 9.4.5 BASELINE DESCRIPTIVE STATISTICS

Gender, age, baseline HAM-A scores, education, race, and baseline biomarker levels.

---

#### 9.4.6 PLANNED INTERIM ANALYSES

None

---

#### 9.4.7 SUB-GROUP ANALYSES

None

---

#### 9.4.8 TABULATION OF INDIVIDUAL PARTICIPANT DATA

N/A

---

#### 9.4.9 EXPLORATORY ANALYSES

N/A

## 10 SUPPORTING DOCUMENTATION AND OPERATIONAL CONSIDERATIONS

### 10.1 REGULATORY, ETHICAL, AND STUDY OVERSIGHT CONSIDERATIONS

#### 10.1.1 INFORMED CONSENT PROCESS

Informed consent is a process that is initiated prior to the individual agreeing to participate in the study and continues throughout study participation. Extensive discussion of risks and possible benefits of study participation will be provided to subjects and their families, if applicable. A consent form describing in detail the study procedures and risks will be given to the subject. Consent forms will be IRB-approved, and the subject is required to read and review the document or have the document read to him or her. The investigator or designee will explain the research study to the subject and answer any questions that may arise. The subject will sign the informed consent document prior to any study-related assessments or procedures. Subjects will be given the opportunity to discuss the study with their surrogates or think about it prior to agreeing to participate. They may withdraw consent at any time throughout the course of the study. A copy of the signed informed consent document will be given to subjects for their records. The rights and welfare of the subjects will be protected by emphasizing to them that the quality of their clinical care will not be adversely affected if they decline to participate in this study. The consent process will be documented in the clinical or research record. To complete the informed consent process at the end of study participation, study staff will inform the subject when his/her participation has come to an end and will document the discussion in the study record.

##### 10.1.1.1 CONSENT/ASSENT AND OTHER INFORMATIONAL DOCUMENTS PROVIDED TO PARTICIPANTS

All consented subjects will be provided a copy of their fully executed informed consent document.

##### 10.1.1.2 CONSENT PROCEDURES AND DOCUMENTATION

Each subject will review the informed consent document with the study coordinator and will be provided time to ask and receive answers to any questions. The name of the person obtaining consent will be documented along with date and time consent was obtained.

#### 10.1.2 STUDY DISCONTINUATION AND CLOSURE

This study will be stopped prior to its completion if: (1) the intervention is associated with adverse effects that call into question the safety of the intervention; (2) difficulty in study recruitment or retention will significantly impact the ability to evaluate the study endpoints; (3) any new information becomes available during the trial that necessitates stopping the trial; or (4) other situations occur that might warrant stopping the trial.”

If at any time during the study the participants are found to be at excessive risk, the study will be terminated. All key research personnel have completed the required human subjects training course. Key personnel include all individuals responsible for the design and conduct of the study.

### 10.1.3 CONFIDENTIALITY AND PRIVACY

Subject confidentiality is strictly held in trust by the investigators, study staff, and the sponsor(s) and their agents. This confidentiality is extended to cover testing of biological samples and genetic tests in addition to any study information relating to subjects. The study protocol, documentation, data, and all other information generated will be held in strict confidence. No information concerning the study or the data will be released to any unauthorized third party without prior written approval of the sponsor. The study monitor or other authorized representatives of the sponsor may inspect all study documents and records required to be maintained by the investigator, including but not limited to, medical records (office, clinic, or hospital) for the study subjects. The clinical study site will permit access to such records. All research material will be treated in a confidential manner, and only research staff will have access to the data. Confidentiality will be maintained by assigning identification numbers for all aspects of the project; all data entered into computer databases will use only this identifier. Data are kept in separate coded REDCap data sets and in locked cabinets in locked rooms at UF with access limited to a small number of study personnel. All clinical and other records have identifying names of participants and relatives removed. Electronic data will be password protected and stored in a database on a secure server that is also password protected, with no patient identifying information. No identifiable individual data are presented in scientific publications. Only research personnel will have access to this data.

### 10.1.4 FUTURE USE OF STORED SPECIMENS AND DATA

These data may be combined with those of future large RCTs. The data may also be disseminated in the format of seminar, abstract, peer-reviewed manuscript, and other forms. The remaining samples may be used for appropriate research upon approval, including the discovery of additional biomarkers.

### 10.1.6 SAFETY OVERSIGHT

The Data and Safety Monitoring Plan for this project will also include monitoring by an independent Data Safety Monitoring Board (DSMB), consisting of an anxiety disorders expert ([name]), a hepatologist

([name]), a statistician ([name]), and a pharmacologist ([name]). These individuals will have no affiliation to the proposed study. The DSMB will review any serious adverse event that is reported within 48 hours. They will also convene annually and at the end of the study to review all adverse events. Adverse events that are serious and unexpected will be immediately reported to the IRB, NIH, and FDA (if warranted). Non-serious unanticipated problems shall be described in annual reports to the IRB and NIH. The DSMB will review the adverse events and discuss any concerns regarding them with the Principal Investigators.

Study progress and safety will be reviewed monthly (and more frequently if needed). Progress reports, including patient recruitment, retention/attrition, and AEs will be provided to the Independent Monitor(s) semi-annually. An Annual Report will be compiled and will include a list and summary of AEs. In addition, the Annual Report will address (1) whether AE rates are consistent with pre-study assumptions; (2) reason for dropouts from the study; (3) whether all participants met entry criteria; (4) whether continuation of the study is justified on the basis that additional data are needed to accomplish the stated aims of the study; and (5) conditions whereby the study might be terminated prematurely. The Annual Report will be sent to the Independent Monitor(s) and will be forwarded to the IRB and NCCIH, FDA, and sponsoring industry collaborator. The IRB and other applicable recipients will review progress of this study on an annual basis.

---

#### 10.1.7 CLINICAL MONITORING

The study team will generate Study Reports for the Independent Monitor and will provide information on the following study parameters: liver function, serious adverse events, and biomarker data.

Study Report tables will be generated only from aggregate (not by group assignment) baseline and aggregate safety data for the study population.

---

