The study coordinator for the proposed project has 6 years of experience and will be trained in all study procedures. She will coordinate the screening of potential participants and will meet with [name] weekly to discuss study progress. [name], a gastroenterologist with expertise in hepatology and liver transplantation, will be responsible for overseeing the medical safety monitoring for this trial. He has extensive experience as a medical monitor for national clinical trials of multiple medications. He will communicate with [name] on a regular basis, and will also communicate any and all adverse events to the data safety monitoring board. He will interpret the results of the liver biochemistries (all results will be blinded to treatment condition) and will be responsible for referring participants to appropriate additional clinical evaluation and intervention if needed.

Effective screening will rule out active medical or psychiatric conditions, including supplement or medication use, chronic alcohol use, and evidence of pre-existing liver disease that may prevent someone from participating in the studies. Once the subject enters the study, an experienced research team will closely follow him or her. The research team has developed considerable expertise in monitoring the safety of subjects participating in research studies. An experienced research psychiatrist and the hepatologist is available 24 hours a day, 7 days a week. If at any point in the procedures symptoms become distressing or dangerous, subjects will be withdrawn from the study and, if necessary, treatment instituted.

This project will be conducted in compliance with research statutes outlined in the Health Insurance Portability and Accountability Act. Each participant will be assigned a unique identification number, and this number will be used to link all subsequent information collected. This file will be secured with password access, since it represents a direct link between the name and identification number of a participant. All paper files and data are kept in locked file cabinets to ensure confidentiality. The other procedures to ensure confidentiality follow the regulations and policies of the University of Florida and UF Health. Data file archival and back-up will be performed on a regular basis. The routine monitoring, maintenance, and quality control of the databases will be the responsibility of [name].

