## 7 STUDY INTERVENTION DISCONTINUATION AND PARTICIPANT DISCONTINUATION/WITHDRAWAL

### 7.1 DISCONTINUATION OF STUDY INTERVENTION

This study will be stopped prior to its completion if: (1) the intervention is associated with adverse effects that call into question the safety of the intervention; (2) difficulty in study recruitment or retention will significantly impact the ability to evaluate the study endpoints; (3) any new information becomes available during the trial that necessitates stopping the trial; or (4) other situations occur that might warrant stopping the trial. If at any time during the study the participants are found to be at excessive risk, the study will be terminated. All key research personnel have completed the required human subjects training course. Key personnel include all individuals responsible for the design and conduct of the study.

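### Safety tables for the monitors are pooled and the DSMB has no described route to data by arm, so stopping criterion (1) cannot be judged during the trial by comparing arms

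*Combined protocol and SAP*

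**What the plan says.** **Reports.** Under 10.1.7 the study team prepares Study Reports for the Independent Monitor covering "liver function, serious adverse events, and biomarker data". The same section then sets their format: "Study Report tables will be generated only from aggregate (not by group assignment) baseline and aggregate safety data for the study population". (Listing biomarker data while limiting the tables to baseline and safety data is a small inconsistency of its own.)

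**Stopping.** Section 7.1, repeated in 10.1.2, ends the trial early if "the intervention is associated with adverse effects that call into question the safety of the intervention". It adds: "If at any time during the study the participants are found to be at excessive risk, the study will be terminated". Neither section gives a threshold, calls for a comparison, or names who decides.

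**Blinding.** Section 6.3 blinds investigators and participants and leaves the list of prepared supplements with the pharmacist. Section 2.3.3 has a hepatologist interpret the liver biochemistries, where "all results will be blinded to treatment condition".

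**Oversight.** Section 10.1.6 sets up an independent DSMB that includes a hepatologist and a statistician. It provides that "The DSMB will review any serious adverse event that is reported within 48 hours" and that "They will also convene annually and at the end of the study to review all adverse events". Progress reports that include adverse events go to the Independent Monitor(s) twice a year. An Annual Report addresses "whether AE rates are consistent with pre-study assumptions". The arm is not mentioned in any of these. Section 9.4.6 plans no interim analysis.

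**The concern.** Criterion (1) is worded as harm associated with the intervention. In a placebo-controlled trial the most direct evidence on that is whether events are more frequent on kava than on placebo. The investigators are blinded, the hepatologist reads liver results blinded, and the only stated table format is pooled. The board has the expertise to read a comparison but is not promised one.

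The main safety question here is the liver. If non-serious enzyme rises gathered in one arm, the reports as described would show a single pooled percentage. The board could then miss a pattern that bears on participants still to be enrolled, or be alarmed by a pooled rate that is evenly split.

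**Working it through.** The plan gives no figure on this point to reproduce. The check is a reading of the routes to a safety judgement, followed by an illustration.

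**Step 1. What each route gives the DSMB during the trial**

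- *Individual SAEs* (8.3.6, 10.1.6): reviewed during the trial. Whether the arm is disclosed is not stated.
- *Non-serious liver-test rises*: these reach the board. Section 8.3.1 counts an abnormal laboratory value as an adverse event, 2.3.3 has the medical monitor pass all adverse events to the board, and 10.1.6 has the board review them all. The arm is missing.
- *Relatedness per event* (8.3.3.2): judged on timing, abatement after stopping, rechallenge and alternative causes. This is weak evidence for this hazard. Dosing lasts one week, whereas 2.3.3 expects symptoms of liver toxicity 2 to 12 weeks after first ingestion, so most would begin after the capsules had stopped. No rechallenge is planned, and the timing is the same for someone who took placebo.
- *Pooled rates against assumptions* (10.1.6): the protocol states no assumed rate for liver-test elevations. Sections 2.2 and 2.3.1 give only liver injury per million daily doses, and 2.2 adds a risk of observing hepatotoxicity by project phase.
- *Comparison by arm*: no route described.

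**Step 2. What pooling can hide**

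Inputs: 26 randomized (9.2). Assumption: 13 per arm. The event counts are hypothetical. With k participants having an event, the chance under no effect that all k fall in one named arm is C(13,k)/C(26,k). The two-sided Fisher p for k v 0 is twice that.

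| Events (pooled) | Even or nearest split | Most lopsided split |
|---|---|---|
| 3/26 = 11.5% | 2 v 1, p = 1.00 | 3 v 0: 2 × 286/2,600 = 0.22 |
| 4/26 = 15.4% | 2 v 2, p = 1.00 | 4 v 0: 2 × 715/14,950 = 0.096 |
| 5/26 = 19.2% | 3 v 2, p = 1.00 | 5 v 0: 2 × 1,287/65,780 = 0.039 |
| 6/26 = 23.1% | 3 v 3, p = 1.00 | 6 v 0: 2 × 1,716/230,230 = 0.015 |

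With 4 or fewer events no split reaches 0.05. With 5 or 6, only the most extreme does (4 v 1 gives 0.322; 5 v 1 gives 0.160).

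Using the 10 expected completers per arm instead, the cut-off is the same: 4 v 0 gives 2 × 210/4,845 = 0.087, and 5 v 0 gives 2 × 252/15,504 = 0.033.

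**Step 3. When a table could act**

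The synopsis gives a study duration of 65 weeks and 13 weeks per participant. 65/52 = 1.25 years, so about one annual DSMB meeting precedes the final one. Enrolment could run for about 65 − 13 = 52 weeks, so that meeting may fall as enrolment closes. The semi-annual reports offer an earlier point.

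**The case against.** The strongest reply is that the plan already has working safety oversight and that a comparison would add little. Much of this stands.

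- *Harm can be judged before the end.* A reader might infer that nobody can apply criterion (1) until the trial is over. The documents do not support that. Causality is assessed event by event throughout, serious events go to the board promptly, related and unexpected serious events go to the FDA, the funder and the safety monitors, and the excessive-risk clause needs no arm data.
- *Enzyme rises are not lost.* A reader might infer that only SAEs reach the board. Sections 8.3.1, 2.3.3 and 10.1.6 together show otherwise; what is missing is the arm label.
- *There is no prohibition.* A reader might take 10.1.7 as barring the DSMB from the allocation. It governs tables produced by the study team, and pooling those protects the blind. The pharmacist holds the list, so unblinding is possible. The protocol does not describe it.
- *The study team may not be fully blind.* Section 6.3 has the coordinator open an envelope that holds the group assignment. That is a separate question about blinding and gives the DSMB no comparison.
- *Information is limited.* With 26 participants, rare liver injury must be judged case by case either way. Section 2.2 puts the risk of observing hepatotoxicity below 0.9% even for the larger of its two project phases.

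What remains is that case-level causality under blinding is weak for a delayed event after one week of capsules, and that the pooled-rate check has no stated benchmark for liver tests. A board also need not wait for p < 0.05: 4 v 0 could prompt questions that 2 v 2 would not.

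**Conclusion.** The gap is real and narrow. The only stated table format is pooled, and no passage gives the DSMB a table by arm or a way to obtain the codes. Criterion (1) can therefore be assessed during the trial from cases and pooled rates, but not by comparing arms. To say that harm cannot be assessed at all, or that the board is forbidden the allocation, would go beyond the text.

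The gain from closing the gap is modest. At 13 per arm, a comparison can reach p < 0.05 only with 5 or more participants affected and a very lopsided split. It is still worth making, because it is cheap, leaves the study team blinded, and addresses the hazard that the monitoring is built around.

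Assumptions: 13 per arm (the cut-off is unchanged at 10), hypothetical event counts, p-values used only as a descriptive scale, and the Independent Monitor of 10.1.7 read as the DSMB or acting for it, which the protocol does not make explicit.

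**What to change.** Amend 10.1.7, with a cross-reference in 10.1.6, as follows:

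1. Keep study-team and open reports pooled.
2. Have the pharmacist give the coded allocation (A/B) to the DSMB statistician, who prepares a closed table of adverse events and liver tests by arm for each semi-annual report and each DSMB review.
3. State that the DSMB may request the meaning of the codes, and how.
4. In 7.1 and 10.1.2, name who applies criterion (1).
5. Say whether the Independent Monitor and the DSMB are the same body.

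The cost is one short table per review and arm codes held by one existing DSMB member outside the study team. The closed table must be kept from the investigators. Sample size, assessments and participant visits do not change.

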#### 10.1.8 QUALITY ASSURANCE AND QUALITY CONTROL

The site SC will ensure that all study personnel have completed all required institution-specific and protocol-specific trainings and that these trainings are documented appropriately on the Training Log. The site SC will also ensure that new personnel are appropriately documented on the Delegation of Responsibilities Log (DOR). While training should be completed and documented in real time, the Lead SC will verify that all training is current and appropriately documented. All study staff will complete CITI or NIH Human Subjects training prior to commencement of study. The investigators are responsible for ensuring the accuracy, completeness, legibility, and timeliness of the data reported. All source documents should be completed in a neat, legible manner to ensure accurate interpretation of data. The investigators will maintain adequate case histories of study subjects, including accurate case report forms (CRFs), and source documentation. All data will be entered into a REDCap (Research Electronic Data Capture) database developed for this project. REDCap is a secure, HIPAA-compliant web-based application designed to support traditional case report form data capture. Data will be exported into a

SAS data set for analysis. Data integrity will be evaluated using descriptive statistics (e.g., means, standard deviations, frequencies, percent, range) appropriate for measurement levels. Checks for implausible or out-of-range values, distributional forms, and missingness will be performed. Data transformations (e.g., Box-Cox family of transforms) and/or cross product terms will be incorporated, if required, based on evaluation of tenability of statistical model assumptions and model fit to the data. All analyses will be conducted using SAS version 9.4 or later.

---

#### 10.1.9.1 DATA COLLECTION AND MANAGEMENT RESPONSIBILITIES

Data collection and accurate documentation are the responsibility of the study staff under the supervision of the investigator. All source documents and laboratory reports must be reviewed by the study team and data entry staff, who will ensure that they are accurate and complete. Unanticipated problems and adverse events must be reviewed by the investigator or designee.

---

#### 10.1.9.2 STUDY RECORDS RETENTION

During this study we will follow NIH, UF IRB, and FDA regulations on study record retention. Should the retention durations differ, we will recognize the longer duration for record retention.

---

#### 10.1.10 PROTOCOL DEVIATIONS

All protocol deviation reporting will follow NIH and UF IRB guidelines.

---

#### 10.1.11 PUBLICATION AND DATA SHARING POLICY

Sharing of data generated by this project is an essential part of our proposed activities and will be carried out in several different ways. We will publish the results of our work in appropriate psychiatric and pharmacological journals. After the publication of the results of the study, clinical data (without identifiers) will be made available to other investigators, if requested. As required by the IRB at UF, participants in our study have the option to choose whether or not they agree to allow their data to be shared with other investigators. In our experience, the vast majority of participants agree to have their information shared with other investigators who are interested in studying neuropsychiatric disorders. We also welcome collaboration with others to further explore kava's clinical potential, its active ingredient(s) and detailed mechanism of action.

Our plan includes the following:

- Presentations at scientific meetings
  - From the projects, it is expected that approximately two to three presentations at scientific meetings would be appropriate in the field of anxiety, biomarker or pharmacokinetics.
- Peer-reviewed publications

- The research results will be prepared for peer-reviewed publication. It is expected that the results from the proposed studies will be the basis for 2 – 4 manuscripts in the R61 phase, including 1) pharmacokinetic characterization of kava and its major ingredients; 2) biomarker changes in response to kava treatment and other clinical results.
- Protocol sharing
  - We agree to share our experimental protocols and data with other researchers who are PIs and co-PIs of NIH grants. The sharing can be arranged through the following approaches: 1) on-line data base with a password that can be released to other researchers through the discussion with the program director; and 2) teleconference with other researchers through the arrangement of the program director.
- Department websites
  - Both multi-PI's department maintain departmental websites that have "News" section and websites for individual faculty. The general clinical trial information will be posted both at the "News" site and the multi-PI's individual faculty website that further detailed information may be requested from the multi-PI.
- Clinicaltrials.gov
  - The trial will be registered at clinicaltrials.gov and will be updated as the trial proceeds.

